## **8.1. Administrative procedures**

### **8.1.1. Collection of demographic data**

Demographic data such as date of birth, sex, race, and ethnicity will be recorded in the participant's CRF.

Collection of sex, race and ethnicity data is necessary to assess and monitor the diversity of the trial participants, and to determine if the trial participants are truly representative of the impacted population.

### **8.1.2. Medical History**

Participant's medical history will be collected and recorded in participant's medical records. Any pre-existing conditions, signs and/or symptoms present prior to study start will be recorded in the eCRF.

## **8.2. Efficacy and/or immunogenicity assessments**

Not applicable for this study.

## **8.3. Safety assessments**

Planned timepoints for all safety assessments are provided in the SoA (Table 2).

### **8.3.1. Physical examination**

Physical examinations will be performed and recorded in the eCRF at the times shown in Table 2.

- A complete physical examination will include, at a minimum, assessments of the (CV, respiratory, gastrointestinal, and neurological) systems. Height (at screening) and weight (at screening and discontinuation) will also be measured and recorded.
- A brief physical examination will include, at a minimum, assessments of the (skin, lungs, CV system, and abdomen [liver and spleen]).
- After screening, any clinically significant abnormal findings in physical examinations should be reported as AEs.

### 8.3.2. Vital signs

Vital signs will be performed and recorded in the eCRF at the times shown in Table 2.

- Vital signs (pulse rate, systolic and diastolic blood pressure, and oral body temperature) will be assessed. Triplicate BP measurements will be performed at screening only. Resting supine blood pressure and pulse rate will be measured using a semi-automatic blood pressure recording device with an appropriate cuff size. The participant should have a minimum resting period in a supine position before pulse and blood pressure measurements of 5 minutes.

### 8.3.3. Electrocardiograms

Standard 12-lead ECG will be obtained as outlined in the SoA (Table 2) using an ECG machine that automatically calculates the heart rate. All ECGs in this study should all be recorded using the same make of ECG device (Mortara Surveyor Telemetry Central and Mortara telemetry transmitters Model: Surveyor S4), with the exception of Screening visit, where CardioSoft® will be used. The Mortara system is validated every 12 months. Monitors will also be available to spot check the calibration when on-site. The readings generated by Mortara surveyor S4 machine will be validated by the cardiologist with their interpretation on whether the findings are significant and related to paroxetine. ECGs must be recorded after 10 minutes rest in the supine position to ensure a stable Baseline. ECGs will be performed and recorded in the eCRF at the times shown in Table 2. The preferred sequence of cardiovascular data collection during study visits is ECG collection first, followed by vital signs, blood sampling, and any remaining assessments for that visit.

At Screening, participants will be excluded based on ECG measurements if the resting QTc is >450msec (mean of three twelve-lead ECG measurements and using Fridericia's correction). The Fridericia QT correction formula (QTcF) must be used for clinical decisions, e.g., at Screening to assess eligibility. Further, all ECGs will be performed in triplicate collected within 5 min, at least 1 minute in between, at each timepoint.

- Triplicate ECGs will be performed at each timepoint as detailed in SOA (Table 2). The mean QTc value will be calculated from the triplicate ECGs for each participant.

- The ECG extractions will be paired with paroxetine concentration samples but will be obtained before the actual paroxetine concentration sampling time to avoid changes in autonomic tone associated with the psychological aspects of blood collection as well as the reduction in blood volume subsequent to blood collection.
- At visits where an ECG is not scheduled, an ECG can be performed if medically indicated.
- All ECG traces will be measured by a third-party vendor, which includes review by a licensed cardiologist. The cardiologist will review the ECGs and provide interpretation on whether the findings are normal, abnormal but non-clinically significant (unrelated to Paroxetine), or abnormal but clinically significant (related to paroxetine).
- More than one cardiologist from the vendor may be reviewing the ECGs in the study. However, to remove bias all ECGs of a particular participant will be reviewed by the same cardiologist. The cardiologists will also be blinded to study visits/timestamps/paroxetine dose at which the ECGs were performed. A copy should be filed in the participant's medical records. Any clinically significant finding observed on the ECG should be recorded as an AE. A copy of ECG traces (with participant-identifying details redacted) may be collected by a Sponsor appointed representative for additional cardiology review if required. Clinically significant abnormalities must be recorded on the eCRF as either medical history/current medical conditions or adverse events as appropriate.

#### **8.3.4. Clinical Safety laboratory tests**

- See [Section 10.2](#) for the list of clinical laboratory tests to be performed in accordance with laboratory manual and the SoA ([Section 1.3](#)).
- The Investigator must review the laboratory results, document this review, and record any clinically significant changes occurring during the study as an AE. The laboratory results must be retained with source documents.
- Abnormal laboratory findings associated with the underlying disease are not considered clinically significant unless judged by the Investigator to be more severe than expected for the participant's condition.
- All laboratory tests with values considered clinically significantly abnormal during participation in the study or after the last dose of study intervention should be repeated until the values return to normal or baseline or are no longer considered clinically significant by the Investigator or Sponsor's Medical Monitor.
  - a. In the absence of a diagnosis, abnormal laboratory findings assessments or other abnormal results the Investigator considers clinically significant will be recorded as an AE or SAE, if they meet the definition of an AE or SAE (refer to [Sections 10.3.1](#) and [10.3.2](#)).
  - b. If clinically significant/any values do not return to normal/baseline within a period of time judged reasonable by the Investigator, the etiology should be identified, and the Sponsor notified.

- c. If laboratory values from non-protocol-specified laboratory tests performed at the institution's local laboratory require a change in participant management or are considered clinically significant by the Investigator (e.g, SAE or AE or dose modification), then the results must be recorded.
- The tests detailed in Table 5 will be performed by the local laboratory and refer to [Section 10.2](#) for more details/

**Table 5      Protocol-required safety laboratory tests**

| Laboratory Tests          | Parameters  |  |
|---------------------------|---|--|
| Hematology         | 
 
• Platelet count
 
  |  |
|                           | 
 
• Red blood cell (RBC) count
 
  |  |
|                           | 
 
• RBC indices 
 
○ Mean corpuscular volume (MCV)
 
○ %Reticulocytes
 
 
 
  |  |
|                           | 
 
• WBC count with differential: 
 
○ Neutrophils
 
○ Lymphocytes
 
○ Monocytes
 
○ Eosinophils
 
○ Basophils
 
 
 
 |  |
|                           | 
 
• Haemoglobin
 
   |  |
|                           | 
 
• Haematocrit
 
   |  |
|                           |   |  |
| Clinical chemistry | 
 
• Potassium
 
• Creatinine
 
• Sodium
 
• Calcium
 
  | 
 
○ Aspartate aminotransferase (AST)/serum glutamic-oxaloacetic transaminase (SGOT)
 
○ Alanine aminotransferase (ALT)/serum glutamic-pyruvic transaminase (SGPT)
 
○ ALP
 
○ Bilirubin (total, direct and indirect)
 
○ Creatinine kinase
 
 |
| Coagulation tests  | 
 
• Prothrombin time (PT), activated partial thromboplastin time (aPTT), international normalized ration (INR),
 
   |  |
| Pregnancy testing  | 
 
• Highly sensitive serum at screening and final follow-up visit and urine on admission human chorionic gonadotropin (hCG) pregnancy test as needed for WOCBP
 
                            |  |

| Laboratory Tests             | Parameters   |
|------------------------------|--|
| Other screening tests | 
 
• Follicle stimulating hormone and oestradiol (as needed in WONCBP only)
 
• Urine alcohol and drug screen to include at minimum: amphetamines, barbiturates, cocaine, opiates, cannabinoids and benzodiazepines, urine creatinine
 
• Serology HIV antibody and p24 antigen test, HBsAg, and HCV antibody
 
 |

NOTES:

1. All events of ALT [or AST]  $\geq 3 \times$  upper limit of normal (ULN) and total bilirubin  $\geq 2 \times$  ULN ( $> 35\%$  direct bilirubin) or ALT [or AST]  $\geq 3 \times$  ULN and international normalized ratio (INR)  $> 1.5$  (if INR measured), which may indicate severe liver injury (possible Hy's law), must be reported to [Sponsor] in 24 hours (excluding studies of hepatic impairment or cirrhosis).
2. If alkaline phosphatase is elevated, consider fractionating.
3. Local urine testing at screening will be standard for the protocol unless serum testing at screening is required by local regulation or IRB/IEC

### 8.3.5. Pregnancy testing

- Women of childbearing potential must perform a urine/blood pregnancy test before the administration of any dose of study intervention. Pregnancy testing must be done even if the participant is menstruating at the time of the study visit. The study intervention may only be administered if the pregnancy test is negative.
- Refer to [Section 8.4.5](#) for the information on study continuation for participants who become pregnant during the study.

### 8.3.6. Study stopping rules, Safety monitoring committee

#### 8.3.6.1. Study Stopping Rules

Participant safety will be continuously monitored by the Sponsor's Medical Monitor, and designated Safety Lead (or delegate) throughout the study. Pertinent findings and conclusions are shared with the product's safety review team for review of the overall benefit-risk profile of the product.

Dependent on regional guidance, any restart following a temporary hold due to stopping rules being met will require prior submission and approval of a substantial Clinical Trial Application (CTA) amendment to the competent authorities.

Dosing will be placed on temporary hold and must be stopped based on full review of all available safety data and discussion with the Investigator if any of the following occur:

- Two or more participants experiencing any Serious Adverse Reaction (SAR) (i.e. a SAE suspected to be at least possibly related to the study treatment(s)

- Two or more participants experiencing an AE which was assessed as severe in intensity (Grade 3) and is considered as potentially related to the study treatment(s).
- One or more participants in the cohort experiencing QTcF interval >500 msec (or QTcF prolongation >60 msec from Baseline)
- One or more participants in the cohort developing a liver-related finding that would stop treatment based on the liver-related AE rules outlined in [Section 10.2](#) considered as drug related
- The Investigator (or designee) and Sponsor considers that the number and/or severity of AEs, abnormal safety monitoring tests or abnormal laboratory findings justify putting the study on hold.

The Sponsor unilaterally requests it.

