| 
 
1. All events of ALT [or AST] <math>\geq 3 \times</math> upper limit of normal (ULN) and total bilirubin <math>\geq 2 \times</math> ULN (<math>> 35\%</math> direct bilirubin) or ALT [or AST] <math>\geq 3 \times</math> ULN and international normalized ratio (INR) <math>> 1.5</math> (if INR measured), which may indicate severe liver injury (possible Hy's law), must be reported to [Sponsor] in 24 hours (excluding studies of hepatic impairment or cirrhosis).
 
2. If alkaline phosphatase is elevated, consider fractionating.
 
3. Local urine testing at screening will be standard for the protocol unless serum testing at screening is required by local regulation or IRB/IEC
 
 |            |

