# Parexel International

GlaxoSmithKline Research & Development Limited  
GSK 219882

Statistical Analysis Plan

	

• Serology HIV antibody and p24 antigen test, HBsAg, and HCV antibody.

--	--

1. All events of ALT [or AST]  $\geq 3 \times$  upper limit of normal (ULN) and total bilirubin  $\geq 2 \times$  ULN ( $> 35\%$  direct bilirubin) or ALT [or AST]  $\geq 3 \times$  ULN and international normalized ratio (INR)  $> 1.5$  (if INR measured), which may indicate severe liver injury (possible Hy's law), must be reported to [Sponsor] in 24 hours (excluding studies of hepatic impairment or cirrhosis).
2. If alkaline phosphatase is elevated, consider fractionating.
3. Local urine testing at screening will be standard for the protocol unless serum testing at screening is required by local regulation or IRB/IEC.

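### The one-participant liver hold in Protocol 8.3.6.1 has no defined trigger, because Section 10.2, which it cites, sets a reporting threshold and no treatment-stopping rule

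*Protocol*

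**What the plan says.** Section 8.3.6.1 of the protocol lists the events that put dosing on temporary hold. Four are counts of participants:

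- "Two or more participants experiencing any Serious Adverse Reaction (SAR"), meaning an SAE at least possibly related to study treatment;
- "Two or more participants experiencing an AE which was assessed as severe in intensity (Grade 3") and potentially related;
- one or more with QTcF above 500 msec, or with a rise over baseline exceeding 60 msec;
- for the liver, "One or more participants in the cohort developing a liver-related finding that would stop treatment based on the liver-related AE rules outlined in", where the place cited is Section 10.2 and the finding must be considered drug related.

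Two further routes need no count. The investigator and sponsor may judge that AEs, or "abnormal safety monitoring tests or abnormal laboratory findings justify putting the study on hold", and the sponsor may ask for a hold unilaterally.

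Section 10.2 is Appendix 2, Clinical laboratory tests. Table 8 Note 1 takes ALT or AST of at least 3 x ULN with total bilirubin of at least 2 x ULN (more than 35% direct), or with INR above 1.5 if measured, and says that such events "must be reported to [Sponsor] in 24 hours". Note 2 suggests fractionating a raised alkaline phosphatase. Note 1 also appears under Table 5 in Section 8.3.4, and in SAP 6.3 ("which may indicate severe liver injury (possible Hy's law), must be reported to [Sponsor] in 24 hours").

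**The concern.** The liver rule borrows its trigger from another section. It fires on a finding that would stop treatment under rules located in 10.2, so 10.2 must say which liver findings stop treatment. It does not.

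The purpose of a one-participant rule is that the first qualifying case holds dosing without debate. The protocol set that count for liver findings, as it did for QTcF, and set two participants for SARs and for severe related AEs. If the trigger is undefined, the first liver case falls back on discretion, and two competent readers could decide the same case differently. The participants are healthy volunteers who are expected to gain no direct benefit (Section 2.3.2), and the study has no IDMC (Section 8.3.6.2). A mandatory safety rule should therefore be usable as written.

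**Working it through.** The plan gives no figure to reproduce. The check is whether any text supplies the missing criterion, and what the other rules do with a single case.

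**1. Does the cited section supply it?** Section 10.2 covers laboratory handling, the test list and three notes. Note 1 attaches its liver threshold to a report, Note 2 concerns alkaline phosphatase, and Note 3 concerns urine testing at screening. None says that treatment stops.

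**2. Does any other section supply it?**

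| Place | Liver content | Stops treatment at a stated level? |
|---|---|---|
| Protocol 5.1 and 5.2 | Eligibility limits (enzymes and bilirubin at most 1.5 x ULN, with an exception for isolated bilirubin) and exclusion of liver disease | No; entry only |
| Protocol 7.1 | AE and physician decision are listed reasons; the one protocol-defined stopping sub-reason is missed doses | No |
| Protocol 7.1.1 | ECG limits only | No |
| Protocol 7.2 | Abnormal laboratory values listed as a withdrawal sub-reason | No threshold |
| Protocol 8.3.4, Table 5 Note 1 | Same thresholds as Table 8 Note 1 | No; 24-hour report |
| Protocol 10.3.2 | A possible Hy's law case is an SAE | No; reporting duty |
| SAP 6.3, Note 1 | Same thresholds | No; 24-hour report |

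Liver treatment-stopping criteria with a stated threshold in the two documents: 0.

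**3. How many count-based hold rules have a defined trigger?** The SAR trigger is defined in the rule together with the SAE definition in 10.3.2. Severe AE is defined by the intensity scale in 10.3.5.2. The QTcF limits are in the rule itself. That is 3 of 4; the liver rule is the fourth.

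**4. What happens with one drug-related possible Hy's law case?** An ALT-led case is an SAE under 10.3.2 and, being drug related, one SAR. It may also be graded severe. Each of those rules needs 2 participants, so either one falls short by 2 - 1 = 1. Any SAR in a second participant would close the gap, whether or not it was a liver event. The QTcF rule does not apply. Without a defined liver trigger, the single case forces no hold, and the judgement-based clause and the sponsor's request remain.

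**5. When could the trigger be observed?** Table 2 of the protocol schedules liver chemistry at screening, at early discontinuation or withdrawal, and at follow-up. Planned dosing including taper runs from Day 1 to Day 31, or to Day 36 with the optional five days at 10 mg. A completer therefore has no scheduled liver result while dosing. A qualifying result would come from an unscheduled test, or from a discontinuation or follow-up sample. Other participants may still be dosing at that point.

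**The case against.** The strongest reply is that the rule has only one possible referent. Note 1 is the only liver event threshold in 10.2, so a sensible site would treat it as the trigger, and the literal reading empties a rule that the natural reading gives effect to. This is plausible and probably close to what was meant. But the rule asks for a finding that would stop treatment, and Note 1 prescribes only a report. The documents also do not show that the sponsor would stop at that level rather than a lower one, such as a marked isolated ALT rise. And 10.3.2 counts ALT only, whereas Note 1 counts ALT or AST.

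The second reply is that little turns on it. Entry limits exclude people with liver disease, liver injury is not among the risks tabulated in 2.3.1, liver chemistry is sparse, the sponsor hears within 24 hours, and the Medical Monitor reviews safety continuously. All of that stands and limits the size of the point.

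Two stronger readings are tempting, and the documents support neither:

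- **That the study cannot stop for a single liver case.** The judgement-based hold expressly covers abnormal laboratory findings, the sponsor can request a hold, and the investigator can withdraw the individual.
- **That the restart condition turns on which rule is met.** Subject to what the region requires, Section 8.3.6.1 states that "any restart following a temporary hold due to stopping rules being met will require prior submission and approval of a substantial Clinical Trial Application", in the form of an amendment. The judgement-based hold is in the same list of stopping rules, so a hold under it carries the same condition. The condition does not separate the two routes.

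**Conclusion.** The point holds as a defect in a stated safety rule: the one-participant liver hold cites a stopping criterion that neither document contains. What is lost is the automatic, reproducible hold at the first case. The ability to hold dosing is not lost, and the primary QTc analysis is unaffected.

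The size is one undefined trigger out of four count-based rules, and a shortfall of one participant before another mandatory rule would act on a single liver case. The documents give no rate for liver events in this setting, so no probability of a missed hold can be stated. The sparse testing schedule suggests that the rule would seldom come into play.

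The conclusion rests on reading the rule literally. If the sponsor confirms that Note 1 is the intended trigger, the protocol still needs to say so. The change should be made, but it is not a reason to doubt the study's primary conclusion.

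**What to change.** **Main edit, Section 8.3.6.1.** Replace the reference to 10.2 with the trigger itself: one or more participants with ALT or AST >=3 x ULN together with total bilirubin >=2 x ULN and >35% direct, or together with INR >1.5 if measured, considered drug related, including results obtained after that participant's dosing has ended.

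**Accompanying edit, Section 7.1.** Add the same threshold as a minimum individual stopping criterion, and add a matching entry to the stopping-criteria sub-reasons in 7.1 and 7.2. The sponsor may set a stricter level; that is a clinical choice, and 8.3.6.1 should then use the same level.

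**Optional.** Align the ALT-only wording in 10.3.2 with Note 1. This affects SAE reporting only, and investigator judgement under 10.3.2 can already class an AST-led case as serious. Whether to add liver chemistry during dosing is a separate clinical decision that this repair does not need.

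**Cost.** Small wording edits through the normal amendment route, including whatever ethics review Section 10.1.1 requires. The thresholds are already in the protocol. No visit, sample or participant is added, and no SAP analysis changes.

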#### **8.3.6.2. Safety monitoring committee**

An Independent Data Monitoring Committee (IDMC) is not required for this study.

### **8.4. Adverse Events (AEs) serious adverse events (SAEs), and other safety reporting**

For definitions relating to safety information see [Section 10.3](#).

The Investigator and any qualified designees are responsible for detecting, documenting, and recording events that meet the definition of an AE or SAE and other safety information and remain responsible for following up [all AEs OR SAEs, considered related to the study intervention or study procedures, or that caused the participant to discontinue the study (see [Section 7](#)). This includes events reported by the participant.

The method of recording, evaluating, and assessing causality of AEs and SAEs and the procedures for completing and transmitting SAE reports are provided in [Section 10.3](#).

All AEs and SAEs will be collected from the first dose of the study until the last visit at the time points specified in the SoA. All SARs related to study procedure or GSK product will be collected from the moment of giving consent until the last visit. SAE reconciliation process will be mentioned in data management plan or in SAE plan

SAEs assessed as related to study participation (e.g., study intervention, protocol-mandated procedures, invasive tests, or change in existing therapy) or related to a GSK product (concomitant) will be recorded from the time a participant consents to participate in the study. Time period and frequency for collecting AE, SAE, and other safety information.

Medical occurrences that begin before the start of study intervention but after obtaining informed consent will be recorded as medical history/current medical conditions, not as AEs.

